Physical Activity (PA) will be measured by activity monitoring devices. All OAs will wear the ActiGraph GT9X Link wireless activity monitor (ActiGraph LLC.), a tri-axial accelerometer, on the non-dominant wrist for 7 consecutive days. The GT9X Link has a sample rate of 30-100 Hz, a dynamic range of $\pm 8G$, 14 days battery life (rechargeable), 180 days/4 GB data storage, and is water-resistant. Data are collected in 1-minute intervals. A sensor determines whether the device is on or off the wrist. The GT9X Link provides objective 24-hour physical activity measures, including steps, energy expenditure, intensity, and participant's position. Accelerometry is a reliable method of assessing free-living physical activity (ICC=0.98)⁷⁵ and has been validated against direct observation, energy expenditure, and sedentary behavior.^{76, 77} ActiGraph accelerometers have been used for data collection in the National Health and Nutrition Examination (NHANE) surveys and are the most commonly used device in research studies.⁷¹ The device display screen can be disabled, so the device does not display the participant's activity (it will show date and time only).

6.3

We will follow the UCF COVID-19 Human Subject Research (HSR) Standard Safety Plan below:

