Body composition will be tested, and all participants will be asked to empty their bladder, remove socks, shoes, and metal objects (e.g., watches, jewelry) before testing. The participants will be instructed to avoid exercise 6-12 hrs, eating 3-4 hrs, and drinking alcohol/coffee 24 hrs before the body composition test. We will obtain weight from a scale. Participants will be asked to stand for 10-15 mins before testing in a standing position or sit for 10-15 min for a seated position or lie down for 15 mins before testing in a supine position. The RA will present a photo of wipe hands and feet using an InBody tissue (optional).

The RA will also present photos of how to place the touch-type electrodes (labeled LT or RT) at the left and right ankles, middle fingers, and thumbs.

The participants will then place the touch-type electrodes to their left and right ankles, middle fingers, and thumbs. They will hold this position for one minute as the Bioelectrical Impedance Analysis (BIA) device; a minute electrical current will be conducted through the body to determine body composition. The participants will then remove the touch-type electrodes from their left and right ankles, middle fingers, and thumbs. The BIA machine is a widely used commercial device that is FDA approved. There are no risks or discomforts associated with the use of bioelectrical impedance analysis.

Participants will then be instructed to wear the ActiGraph GT9X Link wireless activity monitor on the non-dominant wrist for 7 consecutive days. Participants can remove the monitor only for imaging studies. Each participant will be asked to continue their normal activities while wearing the device. Written instructions will be provided to participants for the use of ActiGraph. The questionnaires and instructions will be provided in English or Spanish by bilingual research assistants (RAs) who will be trained and randomly monitored to ensure quality and consistency in administering questionnaires and tests. Participants will be

provided a phone number for the study team if they have questions about using the activity monitoring device.

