Lastly, participants will be asked (using our evaluation form) about their reactions to the questions and technology (i.e., what they thought about the questionnaires and technology) and let them describe any concerns or problems in wearing the device (e.g., uncomfortable to wear during walking). We will provide feedback on the BBS and BIA test results, and participants will receive \$30 Walmart gift card upon completion of the study.

After 7 days of wearing ActiGraph, the participants will return the monitoring device via mail (we will provide pre-paid mailers) or schedule a date/time for picking it up. Participants will leave the device in front of their place.

- Please see Appendix A for a demographic survey
- Please see Appendix B for the Memory Impairment Screen (MIS)
- Please see Appendix C for Patient Health Questionnaire-9 (PHQ-9)
- Please see Appendix D for the Geriatric Anxiety Inventory-Short form (GAI-SF) and Day-to-Day Experiences with the trait Mindful Attention Awareness Scale (MAAS).
- Please see Appendix E for Short Fall Efficacy Scale International (short FES-I) and behavioral changes related to fear of falling
- Please see Appendix F for hand-grip strength test and static balance performance test
- Please see Appendix G for dynamic balance performance test (Sit to stand) and
- Please see Appendix H for Bioelectrical Impedance Analysis (BIA)
- Please see Appendix I for ActiGraph GT9X Link wireless activity monitors and the Rapid Assessment of Physical Activity (RAPA)
- Please see Appendix J for Evaluation form of acceptability of technology and procedures and the short version of Senior Technology Acceptance

6.5 *NA*, No plan for long-term follow-up in this study.

6.6 *NA*

7.0 **Data and Specimen Banking***

NA

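### Section 6.4 does not fix whether balance and body-composition feedback comes before or after the 7-day activity wear, so it may precede measurement of the PA outcome

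*Combined protocol and SAP*

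**What the plan says.** The relevant text is in section 6.4 (Experimental procedures for both groups), in this order:

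1. Balance, grip strength, sit-to-stand and body composition are tested.
2. The monitor is issued: "Participants will then be instructed to wear the ActiGraph GT9X Link wireless activity monitor on the non-dominant wrist for 7 consecutive days".
3. A closing paragraph covers the evaluation form, in which participants "describe any concerns or problems in wearing the device (e.g., uncomfortable to wear during walking"), then the feedback ("We will provide feedback on the BBS and BIA test results"), and, in that same sentence, a "Walmart gift card upon completion of the study".
4. A new paragraph opens with "After 7 days of wearing ActiGraph, the participants will return the monitoring device via mail", or a pick-up is arranged, for which "Participants will leave the device in front of their place".

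No section gives the day or visit of the feedback. Sections 1.0 and 13.5 describe 9 days with two visits, and section 13.5 ties the gift card to the end of the second visit, whose content is nowhere set out. Section 8.1 says that results will not be shared directly with participants.

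The plan does guard against reactivity elsewhere. Section 6.2 notes "The device display screen can be disabled, so the device does not display the participant's activity", and section 6.4 adds "Each participant will be asked to continue their normal activities while wearing the device".

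**The concern.** Section 6.1 treats accelerometer PA as a consequence of FRA, and Aim 2, the primary objective, compares PA across the four FRA groups. The BBS result is one of the two axes that define those groups. If it is fed back before or during the wear week, the outcome is measured after participants have been told part of their own group definition. The message also differs by group: poor balance for incongruent and congruent participants, normal balance for rational and irrational ones.

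The protocol's own reasoning makes a reaction plausible. Section 3.3 holds that unfounded fear keeps irrational participants inactive, and that incongruent participants are less cautious than they should be. A balance result speaks to both beliefs. On that reasoning the first group might move more and the second less during the week in which activity is recorded. What is at stake is whether a PA difference between groups reflects FRA or partly reflects the feedback.

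**Working it through.** The plan gives no figure on this point, so there is nothing to reproduce. The check is mainly a reading of the passages side by side.

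**Signs that feedback precedes the end of wear**
- Section 6.4 mentions it after the monitor is issued and before the paragraph on the end of the 7 days.
- Return is by mail or doorstep pick-up, so section 6.4 describes no face-to-face contact after wear.

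**Signs that feedback follows wear**
- The same paragraph asks about problems wearing the device, which presupposes some wear.
- The feedback sentence goes on to the payment made on completion.
- Section 13.5 places that payment after a second visit. Section 22.1 puts consent, surveys and tests at the first visit. Nine days fits 1 + 7 + 1: a visit, the wear week, a visit. This is an inference.

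Neither set settles the timing, and no sentence requires results to be withheld until wear ends.

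**Would the planned analysis absorb an effect?** Section 17.1 adjusts, where feasible, for age, sex, day order, wear time and fall history, with further health variables added one by one. None represents feedback or its timing. Day order can pick up a trend over the week that is common to all groups. It cannot remove a group-specific shift present on every day.

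**Which Aim 2 comparisons are exposed?** Only those with PA as outcome. FRA group and body composition at timepoint 1 are measured before any feedback.

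**Scale, by assumption.** The documents give no reactivity figure. Inputs: 30 per group (section 6.4 target); two-sided alpha 0.05 and power 0.80 (section 17.1, where they are stated for a different comparison); a differential shift b of 0.1 to 0.3 SD in PA between two groups (assumed).

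- Standard error of a difference in SD units: √(1/30 + 1/30) = 0.2582.
- Detectable difference: (1.960 + 0.842) × 0.2582 = 0.72 SD (0.74 by the t distribution).
- False-positive rate with no true difference: Φ(−1.960 + b/0.2582) + Φ(−1.960 − b/0.2582).
- Power when the shift opposes a true 0.723 SD difference: Φ((0.723 − b)/0.2582 − 1.960).

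| Assumed shift b (SD) | b / 0.723 | False-positive rate | Power if opposed |
|---|---|---|---|
| 0 | 0% | 5.0% | 80% |
| 0.1 | 14% | 6.7% | 67.5% |
| 0.2 | 28% | 12.1% | 52.7% |
| 0.3 | 41% | 21.3% | 37.4% |

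The table shows what a shift of that size would do. It is not evidence that one occurs.

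**Timepoint 2.** About 60 of the 120 return (section 13.1). Whether timepoint 1 feedback is given on the first or the last of the 9 days, it comes before their timepoint 2 fear-of-falling, balance, body-composition and PA measures.

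**The case against.** The strongest reply is that the closing paragraph of section 6.4 describes the closing visit. Questions on wear experience, feedback and the completion payment belong together, and section 13.5 confirms that a second visit exists. Text order is weak evidence: section 6.4 describes sit-to-stand twice, and the revision history shows that the return of the device by mail or pick-up was added in the 02/01/2021 modification, which may be why it comes last. The evaluation form (Appendix J) and the operation manual listed in section 9.0 are not in the documents and may settle the matter.

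Much of this stands. A reader might infer that the protocol places feedback before wear and that the PA outcome is therefore biased. The documents do not support that. The timing is open, and nothing in them shows that feedback changes activity or in which direction. The balance message also has two levels, not four. Rational and irrational participants are both told their balance is normal, so a bias between those two groups needs a different response to the same message.

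What the reply does not remove is the absence of any rule. Two staff members could follow the two readings in good faith, and no feedback date would be recorded to show which was followed. Section 8.1 adds to the doubt: it conflicts with section 6.4 unless it refers only to aggregate study findings.

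**Conclusion.** The point holds as an unspecified sequence with a plausible consequence for the primary PA comparison. It is not a demonstrated bias. Feedback before or during wear is permitted by the text as ordered, and the planned covariates would not correct a constant group-specific effect. Direction and size are unknown. The rise in false-positive rate to between 6.7% and 21.3%, and the fall in power to between 67.5% and 37.4%, rest wholly on an assumed shift of 0.1 to 0.3 SD, 30 per group and a single unadjusted pairwise comparison.

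A reader might also infer that delaying feedback would protect Aim 3. It would keep fresh feedback out of the timepoint 2 wear week. It would not remove carry-over from timepoint 1 feedback, which exists under either reading.

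The change is worth making because it is cheap and closes the one route to reactivity that the plan leaves unguarded.

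**What to change.** - In section 6.4, state that individual BBS and BIA results are withheld until the 7-day wear is complete and the device has been returned, and are then given at the second visit, by phone or by mail. Apply the same rule at timepoint 2.
- Record the date of feedback for each participant, so that adherence to the sequence can be checked.
- Reconcile section 6.4 with section 8.1, for example by saying that section 8.1 concerns aggregate study results, if that is what is meant.
- In the Aim 3 analysis text (section 17.1), acknowledge that timepoint 1 feedback precedes all timepoint 2 measures and limits the interpretation of change between timepoints.

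Cost: a few sentences, one recorded date per participant and timepoint, and feedback delayed by about a week. No visit is added.

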8.0 Sharing of Results with Subjects*

8.1

There are no plans to share the results for this study directly with the participants because the results have no direct benefits to the participants. The results of this study will be published in journals and provided to participants upon their request.

9.0 Study Timelines*

Participants will need about 105-158 minutes (total) to obtain consent and complete the questionnaires (e.g., socio-demographic, FOF, PHQ-9, fall risk, frailty, social network), the static and dynamic balance performance tests, body composition testing, learn how to wear the ActiGraph GT9X Link wireless activity monitor, and to complete the evaluation form of acceptability of technology and procedures.

Table 2. Timeline of activities and tasks to be accomplished during the proposed 2-year grant period

Activity	Year Month	1												2											
		1	2	3	4	5	6	7	8	9	10	11	12	1	2	3	4	5	6	7	8	9	10	11	12
Convene team, develop a study operation manual, staffing training, and set up database		█	█	█																					
Screen, recruit, enrollment, inform consent, data collection, follow-up, and data management					█	█	█	█	█	█	█	█	█	█	█	█	█	█	█	█	█	█	█	█	█
Interim analyses										█	█	█	█	█	█	█	█	█	█	█	█	█	█	█	
Final analyses																									
Dissemination and final grant report																									

10.0 Inclusion and Exclusion Criteria*

10.1

We will screen individuals who will be eligible to participate based on the inclusion and exclusion criteria listed

10.2

Participants will be enrolled if they meet all of the following inclusion criteria: 1) ≥ 60 years of age; 2) no marked cognitive impairment [Memory Impairment Screen (MIS) score ≥5], 3) speak English or Spanish, and 4) live in Kinneret Sr. Apartments.

Exclusion criteria:1) a medical condition precluding balance test (e.g., unable to stand on the balance plate) and/or PA (e.g., shortness of breath; feeling pressure when performing PA); or 2) currently receiving treatment from a rehabilitation facility, or 3) have a metal implant.

10.3

We will exclude all the special populations:

- Adults unable to consent
- Individuals who are not yet adults (infants, children, teenagers)
- Pregnant women
- Prisoners

11.0 Vulnerable Populations*

NA (This study will not include any vulnerable populations such as cognitively impaired adults, children, pregnant woman or prisoners)

12.0 Local Number of Subjects

12.1

About 120 participants for timepoint 1, 60 participants for timepoint 2.

13.0 Recruitment Methods

13.1 *Describe when, where, and how*

Approximately 150-200 older adults in Central Florida and Kinneret Sr Apartments will be screened to enroll 120 older adults in this study.

For the Kinneret Sr Apartments, staff from this site will introduce the researchers to older adults for performing recruitment. Our team will meet with participants in a common room or a meeting room in Kinneret Sr Apartments for screening participants.

In the general population, we will recruit them via social media, flyers, and word of mouth.

The research team will follow the UCF COVID-19 Human Subject Research Standard Safety Plan and maintain a log that tracks screening, eligibility, contact, and recruitment.

Approximately 60 adults of the 120 adults who participated at timepoint 1 will be contacted for enrollment for timepoint 2. We will contact participants who elected to be contacted for future studies in their original consent form.

13.2 *Source to subjects*

-Kinneret Sr Apartments, Orlando, FL (Please see Table in Section 24 for the source of subjects).

-General population who are living in Central Florida

13.3 Methods that will be used to identify potential subjects

In recruitment at the Kinneret Sr Apartments, authorized representatives will coordinate and support us as we participate and recruit within this site. They will introduce our team to their staff and older adults for performing the initial screening and determining study eligibility. [name] (PI) has created continuing relationships with staff in this site in our previous study.

In the general population, we will recruit them via social media, flyers, and word of mouth. Potential subjects who want to participate in this study will contact us via email or phone.

13.4 Describe materials that will be used to recruit subjects

We will post an advertisement for participants screening in the form of a flyer on the public boards (in dining rooms, entrances, elevators) and social media. See the printed advertisement.

13.5

All 120 participants are estimated to complete the study, and they will be enrolled in this study for 9 days with two visits. The participants will receive \$30 Walmart gift card after they are done with the second visit. If participants withdraw from the study, they will not receive them. All 60 participants are estimated to complete the second timepoint assessment, and they will be enrolled in this study for 9 days with two visits. The participants will receive \$30 Walmart gift card after they are done with the second visit. If participants withdraw from the study, they will not receive them.

14.0 Withdrawal of Subjects*

Participation is entirely voluntary. The participants can withdraw from the study at any time without consequences of any kind. However, responses of participants that were submitted, and the data recorded will not be excluded from the analysis. The primary investigator also reserves the right to withdraw participants at any time without their approval.

15.0 Risks to Subjects*

15.1

The risks to participants are minimal and do not exceed the risks associated with activities found in daily life. Minimal risk of fatigue may occur related to the balance performance test, sit to stand test, bioelectrical impedance analysis test, and wearing an activity monitoring device. They will be encouraged to stop the test and rest in the area, which will be provided in the test area. In addition, the participant needs to answer the Patient Health Questionnaire-9 (PHQ-9), a 9-item survey, which includes questions about depressive symptoms. If they have a higher score (A score ≥ 10 points), which is suggestive of depression, the researcher will advise and recommend them to seek a comprehensive assessment with their doctor. The cost for any treatment will be billed to the participant or their medical or hospital insurance.

15.2 NA

15.3 NA

15.4 NA

16.0 Potential Benefits to Subjects*

16.1

There is no direct benefit to the participants in this study

16.2 NA

17.0 Data Management* and Confidentiality

17.1

Data Analysis. All analyses will be performed in SPSS version 25 or SAS version 9.4 with sufficient annotation for reproducibility. Descriptive and exploratory analyses will be performed first to investigate distributional assumptions. Although no differences are hypothesized, descriptive subgroup analyses by sex will be conducted.

Aim 1. Examine the feasibility of recruitment, especially during the COVID-19 pandemic and acceptability of technologies and procedures for use among OAs in low-income settings. We will assess the ability to recruit the sample by calculating the proportions of low-income OAs: (a) recruited out of the total screened, and (b) who completed all study procedures. We will track the number of days and time spent to recruit the sample. The results will inform planning for future larger studies. The acceptability of the technologies and procedures will be examined based on an evaluation form (e.g., what they thought about the questionnaires and technology) and their recommendations. We will identify code, categorize participants' responses, and determine the frequency for each category. Demographic data, including essential characteristics of OAs will be obtained for study participants. We anticipate no

more than 3% missing values on any one item, as data will be collected in person on-site.

Aim 2. Examine the associations among fall risk appraisal, body composition, and physical activity.

Aim 2 hypotheses are: **1)** Rational FRA is associated with higher levels of PA and skeletal muscle mass, and lower levels of percent of body fat and BMI, **2)** Incongruent FRA is associated with higher levels of PA and skeletal muscle mass, and lower levels of percent of body fat and BMI, **3)** Irrational and congruent FRAs are associated with lower levels of PA and skeletal muscle mass, and higher levels of percent of body fat and BMI. General summary statistics will be presented for continuous data, and percentages will be presented for categorical data. Participant demographic data will be summarized. Analyses will be performed without adjusting for any covariates, followed by the analyses adjusted for age, comorbidities, depressive symptoms, and fall history. Age, the number of comorbidities and the number of falls in the past year will be selected as covariates in the selected model because of their association with FRA, body composition, and PA. Data from InBody770 (e.g., BMI) and ActiGraph (e.g., steps/day) could be modeled as continuous.

Regression models or one-way ANOVA will be used to examine differences in continuous variables (e.g., BMI, steps/day) across the four groups (rational, incongruent, irrational, and congruent FRAs), and categorical variables (e.g., comorbidities) will be tested using Chi-Squared tests. Rational FRA group will set as a base group, and the other three groups (incongruent, irrational, and congruent FRAs) will be compared with this base group. Whenever feasible, models will be adjusted for age, sex, day order, wear time (minutes/day), and the number of fall history. These following variables will add one by one to evaluate the role of each: mobility problems (Y/N), depression (score or category), fall risk (high/low), perceived general health (score of category), medication use (Y/N), and comorbidities (Y/N). A final model will include all significant potential variables to evaluate whether associations between FRA, body composition and PA, whenever feasible.

Specific Aim 2 Sample Size and Power Analysis. There is no historical precedent and limited information to inform the sample size for this study; therefore, the sample size estimate was based on the variable of the BBS score in our pilot study. The standard deviations of the mean BBS scores in our pilot study were 7.91 in the high PA group and 7.78 in the low PA group (PA by self-report), assuming a two-tail alpha 0.05 and a power 0.8, the estimated total sample size N=120 would allow to sufficiently detect a mean difference about 5 between the two groups. Furthermore, to be able to compare the effect sizes of the different body composition and PA measures, we will perform post-hoc analyses to compare the mean values between the two groups of PA, adjusted for the age group.

Aim 3. Determine the dynamic relationships between fall risk appraisal, body composition, physical activity and behavioral changes related to fear of falling

We hypothesize that higher percentage body fat, and lower frequency and duration of physical activity are associated with fall risk appraisal and the associations vary between four groups. We will collect data at the 2nd timepoint and then a dynamic prediction model will be used to investigate their temporal, dynamic associations.

17.2

We will maintain a master list that will contain identifiable data and links the subject ID codes with the participant's information. The electronic version of this master list will be encrypted, password protected, and stored on a computer and is located in a restricted access room at the College of Nursing. The master list is the only document with identifiable data.

All research data, including identifiers and linking sheets, will be retained for at least 5 years after the study closure.

The de-identified data (such as balance performance test data will be password protected, encrypted, and stored on computers and external hard drives in the restricted access laboratory). The de-identified data will be kept indefinitely. The reason for keeping the de-identified data indefinitely is for scientific reproducibility and transparency.

17.3 NA

17.4

Efforts will be made to limit the use and disclosure of participants' personal information, including research study to people who have a need to review this information. We cannot promise complete secrecy.

Organizations that may inspect and copy our information include the IRB and other representatives of this organization. Research records will be kept in a locked file in the PI's locked office; only the researchers will have access to the records. The researchers will maintain a computer encrypted, a password-protected master list that will contain identifiable data that links the subject ID codes with their information.

